7.3. SAFETY POPULATION

The Safety population (SAF) is the group of subjects who were randomized and received at least one dose of double-blind study drug. The FAP and the Safety populations are identical.

7.4. PROTOCOL DEVIATIONS

Protocol deviations will be identified in several ways: through programmatic checks, through medical reviews, and by clinical research associates during site monitoring. The protocol deviations include but are not limited to:

- 1.) Exclusionary medical history at screening
- 2.) Violation of sodium criteria at screening or at admission to surgery
- 3.) Prior, concomitant, or supplemental medication deviations
- 4.) Violation of inclusion/exclusion criteria related to the pain intensity scores
- 5.) Other known violation of inclusion/exclusion criteria
- 6.) Deviations with respect to concomitant analgesic rescue medication

At the BDRM, protocol deviations will be classified as minor or major and whether they would affect efficacy sufficiently to exclude the patient from the PP population.

8. GENERAL STATISTICAL CONSIDERATIONS

This SAP contains a detailed description of the analytical variables and the statistical methods/procedures that will be presented in support of this clinical study (CLIN2002-PO). Any modification to the proposed analyses will be documented in the integrated statistical/clinical report. Additionally, any exploratory analyses not described in the Statistical Analysis Plan will be documented in the integrated statistical/clinical report.

The overall objectives of this study will be achieved through descriptive and/or inferential analyses involving the efficacy and safety variables collected in this study. All variables specified in the protocol will be reported in listing format. All such variables (other than those used purely for screening purposes) and resulting change from baseline values will be summarized using descriptive statistics for each treatment group. Selected change from baseline values will be compared between the treatment groups statistically. Within this general framework, attention is called to variables that will be used to evaluate the primary hypothesis, pre-specified secondary hypotheses, and additional hypotheses of special interest.

The primary population for efficacy analysis will be the FAP population. Sensitivity analyses based on the PP population will be conducted for the primary efficacy variable if greater than or equal to 20% of FAP patients are excluded from the PP population. The primary population for safety analysis will be the safety population (see Section 7.0 for definitions)

All hypothesis tests comparing CR845 and placebo will be two-sided and conducted at the 5% significance level, unless otherwise specified.

All summary tables will be presented by treatment group (if applicable) and over all patients in the analysis population being summarized. Continuous variables will be summarized using the following descriptive statistics: n, mean, SD, median, minimum, and maximum. Categorical variables will be summarized using counts and percentages. Unless specified otherwise, percentages presented will be calculated using all patients in the analysis population being summarized (with randomized or received treatment as/if appropriate) as the denominator.

SAS® Version 9.2 or later will be used to produce all statistical tables, listings and figures to be contained in Section 14 of the integrated statistical/clinical report.

8.1. ADJUSTMENTS FOR COVARIATES

All statistical analyses of efficacy variables comparing CR845 versus placebo will be adjusted by the location of the primary OA joint (hip vs knee) unless otherwise specified.

Statistical models without repeated measures which compare the change from baseline endpoints will additionally be adjusted for the value observed at baseline prior to first dose of treatment and effect of the study center.

Mixed Models with Repeated Measures (MMRM) comparing results which are included across all time-points will additionally be adjusted for the baseline value, week, treatment by week interaction and the effect of the patient.

8.2. HANDLING OF INCOMPLETE OR MISSING DATA

No missing or incomplete safety data will be imputed.

Weekly Mean Pain Intensity Scores

If a patient reports at least 3 days with non-missing pain intensity scores within a particular week, the weekly mean pain intensity score will be derived using the non-missing scores only. This is identical to imputing the missing scores as the mean of the non-missing scores. If the patient reports less than 3 days with non-missing pain intensity scores within a particular week, the weekly mean pain intensity score will be treated as missing data.

Missing weekly mean pain intensity scores will be imputed using multiple missing data and pattern mixture methodology as detailed in Section 10.1. Sensitivity analyses will be conducted exploring different patterns for missing data. An MMRM will be performed using only observed data without multiple imputation and an analysis using the change from baseline to the last non-missing weekly mean pain intensity score will also be provided.

WOMAC Index Total Score and WOMAC Pain Intensity, Stiffness and Function Sub-Scale Scores

If at least 50% of items within a subscale are non-missing, the missing items of the WOMAC score at a weekly visit will be imputed using the mean of non-missing items within the same subscale. Otherwise, the item, the subscale score and the total score will all remain missing. The total and subscale scores will be derived as the sum of all respective observed and imputed scores. If all values of a particular subscale are missing at a particular week then the total and corresponding subscale score will be treated as missing.

An MMRM will be performed using only observed data for WOMAC related endpoints.

Treatment Pain Response

Patients with a missing weekly mean pain intensity score for Week 8 will be assumed to be a non-responder and assigned a pain response of 0%.

Rescue Medication

If the patient recorded that they did not confirm rescue medication was taken on a particular day, yet the number of tablets was recorded, it will be assumed rescue medication was taken.

All other efficacy endpoints

Missing data will not be imputed.

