11. STATISTICAL METHODS

11.1 General Considerations

The following section summarizes the statistical methods that will be used in the analysis of the clinical data from this study. A statistical analysis plan (SAP) with further detail will be developed and finalized prior to unblinding of the study. If differences occur between analyses described in the final SAP and the current protocol, those found in the SAP will assume primacy.

Unless otherwise noted, continuous variables will be summarized using the number of non-missing observations, mean, standard deviation, median, minimum, and maximum; categorical variables will be summarized using the frequency count and the percentage of patients in each category. In addition to the descriptive summaries, pertinent data listings will be provided to facilitate case studies.

Statistical significance will be declared for all hypothesis testing if the unadjusted 2-sided probability value is < 0.05. Tests for interaction among the sites will be performed at the 0.1 alpha level. All computations will be performed using SAS® (Version 9.2 or higher).

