11.8.1 Secondary Efficacy Variables

Western Ontario & McMaster Osteoarthritis (WOMAC) Index

The change from baseline in the WOMAC Index total score will be analyzed using an MMRM with treatment (placebo vs CR845) and treatment-by-week interaction as fixed effects, baseline value and OA joint (hip vs knee) as covariates, and patient as a random effect. The primary comparison between groups will be based on estimates and contrasts for the weeks 4, 6, and 8 means. The comparison at week 8 will be viewed as secondary. A 95% CI will be constructed for the weeks 4, 6 and 8 mean differences between CR845 and placebo based on the MMRM.

The MMRM model will be implemented using SAS PROC MIXED. REML will be used. An appropriate covariance matrix will be used to model the within patient errors. The use of an unstructured covariance matrix structure as well as other structures, such as spatial patterns, that require fewer parameters (Toeplitz, autoregressive [1], or compound symmetry) will be

examined. The Kenward-Roger approximation will be used to estimate the denominator degrees of freedom and adjust standard errors.

Data missing after early discontinuation will be treated using the same pattern mixture methodology as the one implemented for the primary efficacy analysis. In addition, an MMRM analysis using observed data only (i.e., no imputation) will be presented.

WOMAC Pain Intensity, Stiffness, and Function Sub-scales

The change from baseline in the WOMAC sub-scales for pain intensity, stiffness and function will be analyzed using an MMRM model similar to the one presented above for the WOMAC index total score. Data missing after early discontinuation will be treated using the same pattern mixture methodology as the one implemented for the primary efficacy analysis. In addition, an MMRM analysis using observed data only (i.e., no imputation) will be presented.

Treatment Pain Response

A patient's pain response to treatment is defined as the percent improvement from baseline with respect to the weekly mean of "average pain in the last 24 hours" pain score during the last week of the Maintenance Treatment Period (Week 8)

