11.9.1 Adverse Events

All reported adverse events will be coded using the current version of the Medical Dictionary for Regulatory Activities (MedDRA). Verbatim descriptions of the adverse event in addition to the SOC and the preferred term (PT) will be included in the patients' data listings.

Data for AEs will be analyzed using the treatment-emergent signs and symptoms philosophy. A TEAE is defined as an AE where:

- onset occurs during exposure to study medication or within 7 days after the last dose of study medication, having been absent prior to receiving study medication, or
- onset reoccurs during exposure to study medication or within 7 days after the last dose
 of study medication, having been present but stopping prior to receiving study
 medication, or
- worsening in severity occurs during exposure to study medication relative to the pre-treatment state, when the AE is continuous.

All reported AEs (whether treatment-emergent or not) will be included in a by-patient AE listing. Only TEAEs will be included in summary tables. Adverse events that occur up to the follow-up visit will be counted as TEAEs. The incidence of TEAEs will be presented by the counts

and percentages of patients with AEs. A patient will be counted only once in the incidence count for a MedDRA PT, although a patient may have multiple occurrences (start and stop) of an event associated with a specific MedDRA PT.

Serious adverse events, AEs that lead to study drug or to study discontinuation, and AEs related to treatment will also be summarized. In addition, a table of TEAEs by severity and of TEAEs occurring in \geq 5% of the patients in at least one treatment group will be presented.

If the severity or relationship to the study drug is missing, a worst-case scenario will be assumed (i.e., it will be set to severe or definitely related relationship). All SAEs will be tabulated overall and by severity and relationship to the study drug.

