10.2. SECONDARY EFFICACY VARIABLE(S)

Change from baseline in the Western Ontario & McMaster Osteoarthritis (WOMAC) Index Total Score at each week

The change from baseline in the WOMAC Index total score will be analyzed using an MMRM with treatment (placebo vs CR845) and treatment-by-week interaction as fixed effects, baseline value and OA joint (hip vs knee) as covariates, and patient as a random effect. The primary comparison between groups will be based on estimates and contrasts for the weeks 4, 6, and 8 means. The comparison at week 8 will be viewed as secondary. A 95% CI will be constructed for the weeks 4, 6 and 8 mean differences between CR845 and placebo based on the MMRM.

The MMRM model (based on observed data) will be implemented using SAS PROC MIXED. REML will be used. An appropriate covariance matrix will be used to model the within patient errors. An appropriate covariance matrix will be used to model the within patient errors until there are no convergence issues in the following order: 1) unstructured, 2) Toeplitz, 3) autoregressive [1], 4) compound symmetry, 5) variance components. The Kenward-Roger approximation will be used to estimate the denominator degrees of freedom and adjust standard errors.

Change from baseline in the WOMAC Pain Intensity, Stiffness and Function Sub-scale Scores at each week

The change from baseline in the WOMAC sub-scales for pain intensity, stiffness and function will be analyzed using an MMRM model similar to the one presented above for the WOMAC index total score.

Treatment Pain Response: Proportion of patients with a X0% improvement from baseline in the weekly mean pain intensity at week 8

The proportion of patients with a response to treatment that is $\geq 30\%$ will be analyzed using logistic regression, including treatment, baseline weekly pain score, and OA joint as independent variables. Site will be included as a random effect. Additionally, the proportions will be compared using a Cochran-Mantel-Haenzel test stratified by OA joint (hip or knee) and

dichotomized baseline weekly pain score (<6.7 , ≥ 6.7). These analyses will be repeated for patients who have a response to treatment $\geq 50\%$.

The cumulative proportion of patients that achieve at least 10%, 20%, 30%, 40%, 50%, 60%, 70%, 80%, 90% and 100% response to treatment will be summarized and plotted for each treatment.

Patient Global Impression of Change (PGIC) at Week 8 or End of Treatment visit

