11.1. ADVERSE EVENTS

Adverse events will be coded using MedDRA. Verbatim description of the adverse events and the MedDRA System Organ Class (SOC) and Preferred Term (PT) for all AEs will be contained in the patient data listings. A separate listing sorted by MedDRA SOC and PT will include all verbatim descriptions associated with each SOC/PT category.

Treatment emergent AEs (TEAEs) will be defined as AEs where onset occurs from the day of first dose of study medication up to and including the 2nd day following the day of last dose of study medication.

All reported AEs (whether treatment-emergent or not) will be included in by-subject AE listings. A separate listing will be created with all the distinct levels of SOC, Preferred Terms and the verbatim investigator description reported in the study. Sorting will be alphabetically by SOC, Preferred Term and then verbatim description.

If the adverse event start date is completely/partially missing, the AE will be considered a TEAE unless the following can be determined:

- The partial AE start date is sufficient to show that the AE started prior to the day of first dose of study drug.
- The AE stop date shows that the AE ended prior to the day of first dose of study drug.
- The partial AE start date is sufficient to show that the AE started after the 2 days following the day of last dose of study drug.

The incidence of TEAEs will be presented using counts and percentages of patients with AEs and tabulated by SOC and PT. SOC will be sorted alphabetically and PT within SOC will be sorted by descending frequency based on the incidence across subjects overall. If a patient has multiple occurrences (start and stop) of an event associated with a specific SOC or PT within a SOC, a patient will only be counted once in the incidence count for the SOC or PT within SOC respectively.

The following specific summary tables will be generated:

- Overall incidence of adverse events
- Incidence of TEAEs by SOC overall and by PT within each SOC
- Incidence of TEAEs related to Treatment by SOC overall and by PT within each SOC
 - If a patient reports two or more adverse events that code to the same PT, the event with the maximum relationship will be included in the table. TEAEs with a missing relationship will be assumed to be treatment related.
- Incidence of TEAEs by Maximum Severity, SOC overall and by PT within each SOC

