12. SUMMARY OF CHANGES FROM PROTOCOL-SPECIFIED ANALYSES

At the time of finalizing this SAP, only the following update has been made in this SAP compared to the Study Protocol V3.0 4th November 2016:

Update 1

Protocol Section 11.7.1 Text:

The baseline score will be calculated as the average of the 4 pain scores collected during the Screening period that qualified the patient for randomization

SAP Section 5.1.1 Text:

The weekly mean pain intensity score will be defined as the sum of non-missing daily "average pain over the last 24 hours" scores reported during that week (Days -7 to -1 [Baseline].... divided by the number of days with non-missing scores for that week.

Reason for update

To ensure the derived baseline derivation of the weekly pain score was equivalent in terms of number of days assessed (i.e. 7 day period using any day with a recorded pain score).

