Table 14.2.1.1.6.3 Change from Baseline in the Weekly Mean of the Daily 24 Hour Pain Intensity (NRS) at Week 8 - Sensitivity Analysis 2: MMRM with MNAR Placebo Based Pattern Mixture Modeling For Stage 2 Full Analysis Population (FAP)

Table 14.2.1.1.7.1 Change from Baseline in the Weekly Mean of the Daily 24 Hour Pain Intensity (NRS) at Week 8 - Sensitivity Analysis 3: Single Imputation BOCF/LOCF Over All Patients Full Analysis Population (FAP)

Table 14.2.1.1.7.2 Change from Baseline in the Weekly Mean of the Daily 24 Hour Pain Intensity (NRS) at Week 8 - Sensitivity Analysis 3: Single Imputation BOCF/LOCF For Stage 1 Full Analysis Population (FAP)

Table 14.2.1.1.7.3 Change from Baseline in the Weekly Mean of the Daily 24 Hour Pain Intensity (NRS) at Week 8 - Sensitivity Analysis 3: Single Imputation BOCF/LOCF For Stage 2 Full Analysis Population (FAP)

Table 14.2.1.1.8 Change from Baseline in the Weekly Mean of the Daily 24 Hour Pain Intensity (NRS) – Descriptive Statistics by Primary OA Joint Full Analysis Population (FAP)

Table 14.2.1.2.1 Responder Analysis of Percentage Improvement from Baseline in the Weekly Mean of the Daily 24 Hour Pain Intensity (NRS) Scores at Week 8 Full Analysis Population (FAP)

Table 14.2.1.2.2 Responder Analysis of Percentage Improvement from Baseline in the Weekly Mean of the Daily 24 Hour Pain Intensity (NRS) Scores at Week 8 by Primary OA Joint Full Analysis Population (FAP)

Table 14.2.2.1.1 Change from Baseline in the WOMAC Index Score Over Time – Descriptive Statistics Full Analysis Population (FAP)

Table 14.2.2.1.2 Change from Baseline in the WOMAC Index Total Score – MMRM Analysis Full Analysis Population (FAP)

Table 14.2.2.1.3 Change from Baseline in the WOMAC Index Total Score Over Time by Primary OA Joint Full Analysis Population (FAP)

Table 14.2.2.2.1 Change from Baseline in the WOMAC Index Pain Intensity Subscale Score Over Time – Descriptive Statistics Full Analysis Population (FAP)

Table 14.2.2.2.2 Change from Baseline in the WOMAC Index Pain Intensity Subscale Score – MMRM Analysis Full Analysis Population (FAP)

Table 14.2.2.2.3 Change from Baseline in the WOMAC Index Total Score Over Time by Primary OA Joint Full Analysis Population (FAP)

Table 14.2.2.3.1 Change from Baseline in the WOMAC Index Stiffness Intensity Subscale Score Over Time – Descriptive Statistics Full Analysis Population (FAP)

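### SAP 12 declares one change from the protocol, but the WOMAC missing-data method, the post-dose TEAE window and sensitivity analysis 3 also changed, undeclared and without a reason

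*SAP*

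**What the plan says.** SAP 12 states that "only the following update has been made in this SAP compared to the Study Protocol" and then lists a single item, the baseline pain score, with a reason for that item alone. Protocol 11.1 allows the SAP to depart from the protocol and settles precedence: where analyses differ, "those found in the SAP will assume primacy".

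- **WOMAC.** Protocol 11.8.1 says, for the total score and again for the subscales: "Data missing after early discontinuation will be treated using the same pattern mixture methodology as the one implemented for the primary efficacy analysis". An observed-data MMRM is to be shown as well. SAP 8.2 says: "An MMRM will be performed using only observed data for WOMAC related endpoints". SAP 10.2 repeats this: "The MMRM model (based on observed data) will be implemented using SAS PROC MIXED". SAP 15.1 lists one MMRM table per WOMAC score, the first being "Table 14.2.2.1.2 Change from Baseline in the WOMAC Index Total Score".
- **TEAEs.** Under Protocol 11.9.1 an event qualifies if its "onset occurs during exposure to study medication or within 7 days after the last dose of study medication". The same section also counts events up to the follow-up visit and has a limb for worsening severity. SAP 11.1 counts onsets from the first dosing day "up to and including the 2nd day following the day of last dose of study medication" and has no worsening limb.
- **Sensitivity analysis 3.** Protocol 11.7.1 specifies multiple imputation: draws resembling baseline for AE exits, and draws resembling same-arm patients still in the study for lack-of-efficacy (LOTE) and other exits. SAP 10.1 specifies single imputation: BOCF for AE exits and LOCF for all other exits.

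**The concern.** A change log that says only one thing changed will be read as complete. Anyone relying on it would assume that WOMAC, the TEAE tables and the third sensitivity analysis follow the protocol. They do not.

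The WOMAC change matters most for efficacy. WOMAC is the first-listed secondary objective. The protocol's main method returns AE and LOTE exits to a baseline-like distribution. The observed-data MMRM assumes missing at random, so it in effect credits patients who leave because of adverse events with the improvement of those who stay. An analysis that the protocol had as an addition becomes the only one.

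For safety, a new onset from the third day after the last dose drops out of every TEAE table, although the follow-up visit exists to look for such events. For sensitivity analysis 3, the assumption for LOTE and other exits is different and imputation uncertainty is no longer carried.

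**Working it through.** **Step 1. Count the changes.** SAP 12 declares 1. Setting the sections side by side:

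| Item | Protocol | SAP | In SAP 12? |
|---|---|---|---|
| Baseline pain score | 11.7.1: the 4 qualifying scores | 5.1.1: all recorded days, Day -7 to -1 | Yes |
| WOMAC missing data | 11.8.1: pattern mixture, plus observed-data MMRM | 8.2, 10.2, 15.1: observed-data MMRM only | No |
| TEAE post-dose window | 11.9.1: 7 days, and to the follow-up visit | 11.1: 2 days | No |
| Sensitivity analysis 3 | 11.7.1: multiple imputation | 10.1, 15.1: single BOCF/LOCF | No |
| Responder model (30%, 50%) | 11.8.1: treatment, baseline, joint | 10.2: adds a random site effect | No |

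That makes at least three substantive undeclared changes and one smaller one. I found no reason for any of them in the SAP text available. Section 8.3 was not in that text, but SAP 6 cites it for the sample size re-estimation.

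**Step 2. TEAE days lost.** The follow-up visit is 7 to 10 days after the last dose (Protocol 9.1.5). Against the 7-day limb, 7 - 2 = 5 of 7 days are lost. Against the follow-up-visit rule, up to 10 - 2 = 8 of 10 are lost. The late events remain in listings, and SAP 11.1 plans a table of non-TEAEs after the last dose. The scope of that table conflicts: the text of SAP 11.1 restricts it to patients taking opioids, while the title of Table 14.3.1.9 in SAP 15.1 has no such limit.

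**Step 3. Internal fit of sensitivity analysis 3.** SAP 10.1 applies LOCF to LOTE exits but keeps a sentence likening their missing data to scores of LOTE patients who remain in the study, which does not describe LOCF. The protocol version is not clean either. Its title says hybrid BOCF/LOCF and its rationale is about LOTE patients, yet its rule imputes LOTE exits from all same-arm patients still in the study, exactly as for other exits.

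**Step 4. Illustration for WOMAC.** The documents give no WOMAC SD, expected improvement or placebo AE-exit rate, so all inputs here are assumed. Take AE exits unrelated to score, with exit rates pC (CR845) and pP (placebo), placebo improvement I and drug effect D, in SD units.

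- Missing at random: week-8 difference = (I + D) - I = D.
- AE exits returned to baseline: (1 - pC)(I + D) - (1 - pP)I.
- Shift in favour of CR845 under the SAP method = (pC - pP) × I + pC × D.

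With D = 0 (equal improvement) and I = 0.5 to 1.0:

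- 15% vs 10%: 0.05 × I = 0.025 to 0.05
- 20% vs 10%: 0.10 × I = 0.05 to 0.10
- 20% vs 5%: 0.15 × I = 0.075 to 0.15

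If exits are spread evenly over 8 weeks, the fractions gone by weeks 4, 6 and 8 are 0.5, 0.75 and 1, averaging 0.75. The average over those weeks therefore shifts by 0.02-0.04, 0.04-0.08 and 0.06-0.11 SD. Earlier exits would move it towards the week-8 figures.

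With a drug effect the shift is larger. Taking D = 0.343, the design effect size in the protocol synopsis and not a WOMAC figure, adds 0.15 × 0.343 = 0.051 or 0.20 × 0.343 = 0.069. The week-8 ranges become 0.076-0.101, 0.119-0.169 and 0.144-0.219 SD.

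The one AE-exit rate in the documents is 4 dizziness discontinuations among 20 patients on 5 mg in the earlier 2-week study (Protocol 4.2.1): 4/20 = 20%, exact 95% CI 5.7% to 43.7%.

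**The case against.** The strongest reply is that Protocol 11.1 expressly lets the SAP differ, and the new methods are openly stated in the SAP body and table titles. That stands against any suggestion of concealment or of an impermissible change. It does not make SAP 12 true: primacy decides which method is run, not whether the change log is complete. SAP 8 promises that modifications will be documented in the report, but that concerns later modifications to the SAP's own analyses.

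The weight is also limited. SAP 8.5 leaves secondary endpoints unadjusted and treats them as material for future hypotheses. The SD figures are weakly anchored: the 4/20 comes from a fixed 5-mg group, whereas here patients start at 1 mg and are titrated on tolerability, so 20% may not transfer. All of this stands.

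Several stronger readings are tempting and are not supported:

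- *The primary result is compromised.* None of these undeclared changes touches the primary estimate.
- *The WOMAC MMRM discards dropouts.* It uses their earlier scores; the issue is the missing-at-random assumption.
- *WOMAC is biased by a known amount.* The formula covers AE exits unrelated to score only. For LOTE exits neither size nor direction can be given.
- *Late adverse events are lost.* They leave the TEAE tables but stay in listings, including one for non-treatment-emergent SAEs.
- *Dropping the worsening limb loses many events.* Protocol 10.2 and 10.2.1 should record most worsening as separately dated events.
- *The protocol's sensitivity analysis 3 should come back.* That would restore its own contradiction.

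**Conclusion.** The statement in SAP 12 is wrong. At least three further changes are undeclared and unexplained, and because the SAP has primacy they will govern. Followed as written, the SAP drops the protocol's main WOMAC missing-data analysis and takes 5 of 7, or up to 8 of 10, post-dose days out of all TEAE tables. Both follow from the text and need no assumption beyond the supplied protocol being the version that SAP 12 compares with. Its title page is not available, but the sentence SAP 12 quotes from Protocol 11.7.1 is there.

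The size of the WOMAC shift is illustrative. The range of 0.025 to 0.15 SD at week 8 needs equal improvement in both arms, AE exits unrelated to score, and the assumed gaps and improvements. A drug effect adds the CR845 AE-exit rate times that effect. A smaller or reversed exit gap would shrink the first term or change its sign. This should be corrected, but it does not threaten the primary conclusion.

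**What to change.** - **SAP 12:** list every difference from the protocol with a reason, including the random site effect in the responder model.
- **SAP 8.2 and 10.2:** restore the pattern-mixture analysis for WOMAC total and subscales beside the observed-data MMRM, and add the tables to SAP 15.1.
- **SAP 11.1:** restore the protocol's post-dose TEAE window, or declare and justify the shorter one. Either way, reconcile the 7-day limit with the follow-up-visit rule in Protocol 11.9.1.
- **SAP 10.1:** keep BOCF/LOCF for sensitivity analysis 3, declare it as a change, and replace the LOTE sentence with one that describes LOCF.
- **Table 14.3.1.9:** give it the same scope in SAP 11.1 and SAP 15.1.

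The cost is SAP wording, a few extra tables and some programming. The imputation program in SAP 16.1 is written for eight weekly pain means and truncates at 0 and 10. WOMAC is collected at weeks 1, 2, 3, 4, 6 and 8, with score ranges of 0-50 (pain, 5 items), 0-20 (stiffness, 2), 0-170 (function, 17) and 0-240 (total, 24 × 10). If the protocol's TEAE window is restored, a few off-drug events will count as treatment-emergent.
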